**CLINICAL TRIAL MASTER PROTOCOL AND INVESTIGATIONAL BROCHURE INFORMATION \***

	Master Protocol	Investigator Brochure: <Specify Drug/Device>	Investigator Brochure: <Specify Drug/Device>	Sponsor Consent Form Template(s)
Version #:				
Version Date:				

This study is investigator-authored (investigator developed the study and is conducting the study at UCI and/or with other non-UCI sites).

**NON-TECHNICAL SUMMARY**

Provide a brief non-technical summary or synopsis of the study that can be understood by IRB members with varied research backgrounds, including non-scientists and non-affiliated members.
The purpose of this research study is to understand how different kinds of exercise affect the human body and the health of the heart and lungs. For example, some people like to exercise continuously for relatively long periods of time while others like to exercise for short periods of time with rest periods in between. Children tend to exercise in frequent bouts of brief exercise interspersed with periods of rest. Also, some people like running or treadmill exercise while others like to work out on stationary bicycles. To date, standard exercise testing is based on a century-old paradigm used predominantly for adults that involves maximal exercise protocols (cardiopulmonary exercise testing—CPET). Moreover, different but widely used exercise modalities such as cycle ergometer and treadmills are currently impossible to compare in children, and this has limited the clinical and research application of such testing in the pediatric age-range. A major premise of our laboratory is that laboratory testing of cardiopulmonary fitness in children should be based on protocols that mimic naturally occurring patterns of exercise in children, rather than those that have been artificially employed to assess maximal efforts in adults. This research project designed to begin the process of systematically identifying protocols can be best used for children and young adults. Participants will exercise in different protocols on a bicycle ergometer or treadmill. This research could lead to improved and more

accurate fitness assessment and pave the way to an improved personalized exercise program in health and illness.

[figure not shown]
## **SECTION 1: PURPOSE AND BACKGROUND OF THE RESEARCH**

1. Provide the scientific or scholarly rationale for the research. Describe the relevant background information and the specific gaps in current knowledge that this study intends to address.

Children are naturally the most physically active human beings, and using exercise has long been viewed as a promising approach for disease diagnosis and therapy. However, exercise testing has not achieved its promise in either clinical application or translational science. One barrier has been in the kind of cardiopulmonary exercise testing (CPET) that is typically used in the pediatric population. Another major barrier has been that CPET in children is done with two different modalities: treadmill and cycle ergometer ("stationary bicycle"). The extent to which these two different types of CPET data are interoperable in children is not known.

Maximal oxygen uptake ( $VO_{2\text{max}}$  or peak) is the current gold standard of CPET in both children and adults. Maximal exercise testing is based on century old concepts informed by the false assumption that physiological systems are integrated to perform maximal efforts. More recently, however, there is a growing body of literature to suggest that maximal exercise testing fails to identify impaired responses that are critical components for diagnosis and therapy in children. First, maximal exercise is rarely seen in natural physical activity. Second, maximal exercise testing depends in large measure on the ability of the child or adult to exercise in a range of activity that is perceived as uncomfortable; consequently, one's ability to reach maximal levels is highly dependent on cognitive choices and not necessarily on physiological determinants. The point of this research is to gather preliminary and pilot data that we will use to more formally test innovative noninvasive approaches to assessing fitness in children. We will explore several promising areas: 1) the ability of a child to rapidly increase the integrated physiological responses necessary to perform physical work; 2) the time required in the sudden transition from rest to exercise (mimicking the need, for example, to escape predation) and then to recover from the exercise; and 3) the interoperability of examining these responses using the two most common modalities of laboratory CPET, treadmill and cycle ergometer. We discovered many years ago that in order to successfully test a child's response to heavy exercise, we needed to use protocols that mimic the stop-start activity of natural physical activity. We developed an exercise protocol that uses ten, 2-min bouts of constant work rate exercise interspersed with 1-min rest. We never formally assessed the on- and off-transients of gas exchange or heart rate in these approved studies. Occasionally, the child did remain on the mouthpiece and we captured gas exchange and heart rate data. An intriguing example that has prompted this proposal is seen in the figure below. The actual oxygen uptake data ( $VO_2$ ) are shown in red. We imposed a predicted response based on equations obtained in adults. Note that the adult predictive equations failed to fit the actual data obtained in the child. **It is clear that pilot and exploratory studies are needed if we are to transform this field and enhance the use of exercise testing in clinical and research child health care. No such pilot data exist that one could use to perform either power analyses or data precision calculations.**

## 10 X 2 Exercise bout: Observed vs. predicted VO2

Our study includes the following procedures and rationale:

- CPET – maximal ramp test was found to correlate with fitness in children and adults. Results of the ramp test would be used to configure the intensity and the exercise bouts protocol.
- Brief exercise protocol – exercise protocol that uses ten, 2-min bouts of constant work rate exercise interspersed with 1-min rest. (n.b., the CPET and “10x2” test will be done on both the treadmill and the cycle ergometer). The **rationale** for this is so we can compare the two types of exercise tests commonly used in children.
- Physical activity questionnaire and Godin Leisure Time Exercise questionnaire – physical activity by questionnaire was found to correlate to cardiopulmonary fitness assessments. By using these validated questionnaires we hope to find correlation to different fitness parameters and hence to use a simple and widely used tool for the pediatric population.

**Rationale:** Questionnaires are commonly used to assess perceived difficulty. Comparing cycle ergometer to treadmill will be an important parameter in determining the interoperability of the two modalities.

- Growth and development questionnaire - Exercise through puberty is of great interest and significant changes are reported among boys and girls.

**Rationale:** Interpreting data from children regarding physical activity depends on an assessment of the developmental stage of each child.

- Dual X-ray Absorbiometry (DXA) - Oxygen consumption highly correlates to lean body mass (as measured by DXA) and better differentiate body composition than total weight or body as index (BMI). In a study done in our lab, we found a very strong correlation between lean body mass and both peak VO2 and extrinsic, size-dependent CPET slopes. Each participant will undergo a DXA scan to determine body composition.

**Rationale:** Exercise responses are determined in large measure by lean and fat tissue

distribution. Determining the interoperability of the two modalities will rest on how each is precisely influenced by lean and fat mass.

- Ultrasound - Recently, the importance of muscle mass (by magnetic resonance imaging, MRI) as a determinant of CPET biomarkers in adolescents was shown. In our study, each participant will be evaluated by ultrasound - non invasive muscle mass measurement shown to highly correlate with MRI (gold standard for muscle mass measurements).
- **Rationale:** Ultrasound provides specificity of muscle mass (i.e., particular groups) not available in DXA assessment.
- Respiratory sensors— The importance of identifying different breathing patterns during rest and exercise can be useful in healthy population as well as in disease and chronic conditions. Breathing patterns (breath rate and volume) will be evaluated by a non-invasive ultrasensititve piezoresistive strain sensors capable of measuring large mechanical strains of the chest during breathing. The sensors have a form factor of a disposable BandAid© and will be worn on the upper torso during rest and exercise.

**Rationale:** Spirometry measurements provide information on breath rate and lung volumes at a specific point in time while the respiratory sensors will provide **continues** breath rate and lung volume data during rest and exercise

Maximal exercise has been the gold standard for 100 years in children; however children with chronic disease are unable to achieve maximum levels, thus diminishing the role of maximal exercise in identifying biomarkers of health and disease. It becomes clear that progressive exercise testing, while suitable for gauging maximal work, is inadequate in attempting to quantify fitness levels in children with chronic diseases or disabilities.. Submaximal exercise testing protocols in which the magnitude and duration of the work rate is characterized by short intervals with varying degrees of difficulty and rest will be able to distinguish a difference among healthy subjects that a maximal cardiopulmonary exercise testing would not be able to predict.

This new approach will yield the data needed to develop a mathematical model characterizing the exercise kinetics in children and young adults.

## 2. Provide relevant preliminary data (animal and/or human).

The PI has been a pioneer in examining on and off transience recovery times as a function of growth and development in healthy children and children with chronic diseases. This laboratory has been responsible for seminal observation showing that kinetics of  $\text{VO}_2$ , heart rate (HR), and Carbone dioxide production ( $\text{VCO}_2$ ) change as a function of growth/maturation as well as disease. These papers have established normative data that can be used for the present study. There is also a growing understanding that the field of pediatrics is transforming from one that deals with acute disease to one that need to deal with environmental changes (e.g. sedentary behavior, physical inactivity) and chronic conditions (e.g. obesity) in the 'healthy children' as well as the of chronically ill children who are facing health impairment across the life span. Exercise testing biomarkers in adult medicine are increasingly seen as predictors of quality of life, exacerbation of disease, and even predictors of mortality. It is clear, however, that the current protocols that are used for exercise testing in children are inadequate and are often unsuitable to the particular disease state of the children that needs it most.

Most of the exercise studies are done on a treadmill or stationary bicycle with no ability to compare these two protocols in the same subject (sometimes done in the same laboratory).

Our most recent research was published in 2014 which was our study on how submaximal slopes of gas exchange and HR variables derived during traditional cardiorespiratory exercise testing were of immense value and perhaps even more useful in evaluate cardiorespiratory function that was the traditional cardiorespiratory test.

We plan now on extending the observation to novel protocols that will permit us to more accurately

define on and off transit and recovery times in relatively brief, fun, exercise testing in children and compare it to young adults.

3. Describe the purpose, specific aims or objectives. Specify the hypotheses or research questions to be studied.

**Primary Aim:**

1. Identify gas exchange kinetics during submaximal exercise bouts and rest periods in different workloads and exercise protocols in children and young adults.
2. To develop a mathematical model to predict and compare gas exchange and heart rate kinetics in response to different protocols of exercise (cycle ergometer and treadmill).

**Exploratory Aims:**

1. Identify accurate workloads for ramp protocols in children based on adult treadmill ramp protocols.
2. Based on # 1, develop a treadmill ramp protocol to assess peak oxygen consumption ( $VO_2$ ) based on known workloads in children and young adults.
3. Study the association between body composition and muscle mass (assessed by ultrasound and DXA) and gas exchange kinetics.
4. Study the association between puberty and gas exchange kinetics.
5. Study the association between physical activity and gas exchange kinetics.
6. Identify breathing patterns during rest and exercise.
7. Based on #6, evaluate optimal sensor position to increase sensitivity and specificity.

4. Describe the primary outcome variable(s), secondary outcome variables, and predictors and/or comparison groups as appropriate for the stated study objectives/specific aims.

Our key outcome variables will be:

**Primary:**

Breath by breath gas exchange (e.g.  $VO_2$ ,  $VCO_2$ , Minute ventilation (VE)) and HR values and kinetics in response to exercise. The raw breath by breath data will be used to derive response times for on transient and off transient exercise bouts and best fit parameters from mathematical modeling.

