#### I. Statistical Considerations (This section is required for Investigator-Authored Research)

1. Statistical Analysis Plan: Describe the statistical method(s) for the stated specific aims and hypotheses. Your analysis plans should match the stated study specific aims and hypotheses in Section 1.
 
 Not applicable: A statistical analysis plan is not appropriate for this qualitative study design. Plan for assessing study results: <Type here> Skip to Section 7.
 
This is a pilot study that is being conducted to identify gas exchange kinetics during exercise bouts and rest periods in different workloads during treadmill exercise and cycle ergometer. From past research of single exercise bout gas exchange kinetics the following theoretical model, has been proposed to describe <math>VO_2</math> as a function of time across the bout:

--

Kp

$$G(s) = \frac{Kp}{1+Tp1*s} * \exp(-Td*s)$$

1+Tp1\*s

Kp= gain/amplitude; Tp1 = time constant; Td = time delay; s=second of exercise bout

The goal of the current research is to apply this functional form to observed kinetics during repeated exercise bout protocols. Evaluation of the fit of this model to observed kinetics will be performed using the system identification toolbox in Matlab. The modules for modeling of nonlinear dynamic systems will be applied which produces parameter estimates of the fitted model based on maximum likelihood and prediction-error minimization (PEM). Applying this curve fitting tool may also give rise to variations in the proposed model that should be considered. Comparisons of Final Prediction Error and Mean Squared Error will be performed to determine the model with optimal fit. In addition, to address the issue of out of sample generalizability, cross validation analyses will also be employed to assess model performance.

A secondary goal to this research is that once a functional form has been established, comparisons of the distributions of the function's parameters (Kp, Tp1, Td) can be made in relation to participant characteristics such as sex, pubertal status, and developmental stages (e.g., children, adolescence, adults). For example, a significant difference in the average time constant (Tp1) would be interpreted as more efficient oxygen consumption and differential adaptation to the physiologic challenge of exercise.

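### The written sex, pubertal and developmental-stage comparison rests on one time constant for onset and recovery together, although on- and off-transient response times are the primary outcome

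*Protocol*

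**What the plan says.** **Onset and recovery as separate targets.** In Section 1, item 4 (Primary), "The raw breath by breath data will be used to derive response times for on transient and off transient exercise bouts", alongside best-fit model parameters. Item 1 lists among the areas of interest "the time required in the sudden transition from rest to exercise (mimicking the need, for example, to escape predation) and then to recover". Item 2 plans to "define on and off transit and recovery times in relatively brief, fun, exercise testing in children and compare it to young adults". The first primary aim in item 3 is to "Identify gas exchange kinetics during submaximal exercise bouts and rest periods in different workloads and exercise protocols in children and young adults".

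**The model and the group comparison.** Section 6.I.1 writes out one model, first order with a delay: a gain Kp, one time constant Tp1 and a delay Td. It is to be applied to repeated-bout protocols. As a secondary goal, once a functional form has been settled, comparisons of the fitted "parameters (Kp, Tp1, Td) can be made in relation to participant characteristics such as sex, pubertal status, and developmental stages". The example given is that "a significant difference in the average time constant (Tp1) would be interpreted as more efficient oxygen consumption and differential adaptation". The table in 6.I.5 reports one Tp1 for each of the five participants fitted so far.

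**The room left open.** Section 6.I.1 also says: "The modules for modeling of nonlinear dynamic systems will be applied". It adds that curve fitting "may also give rise to variations in the proposed model that should be considered", with candidates ranked by final prediction error (FPE), mean squared error (MSE) and cross-validation. Section 6.I.2 estimates means and SDs of response times. Section 6.I.3 regresses the primary outcomes on physical activity and puberty level.

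**The concern.** A linear first-order model has the same time constant going up as coming down. Fitted to bouts and rests together, Tp1 is a weighted blend of onset and recovery speed. A group difference in recovery alone then moves Tp1 and, on the protocol's own example, would be read as a general difference in oxygen-uptake efficiency. Faster onset combined with slower recovery can leave Tp1 unchanged, so two real differences show as none.

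Recovery matters here: Section 7.C.2 names failure to recover from a preceding short bout as what could limit a child with chronic disease. The primary outcome already separates the phases, but the sex and developmental-stage comparison that is written down does not draw on it.

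**Working it through.** **Step 1: the plan's own figures.** In the 6.I.5 table RMSE = √MSE: √0.0806 = 0.2839, √0.2393 = 0.4892, √0.0681 = 0.2610, √0.1194 = 0.3455, √0.09144 = 0.3024. All five agree. Mean Tp1 is (52.33 + 49.012 + 48.352 + 67.049 + 55.46)/5 = 54.4 s and the SD is 7.6 s. The 95% chi-square limits for the SD on 4 df are 4.6 to 21.8 s.

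**Step 2: set-up.** From Session 1B (Section 6.C.1): ten bouts of 120 s with 60 s rests, so 10 × 180 = 1,800 samples at 1 s. The true response moves as y(t+1) = target + (y(t) − target)·exp(−1/τ), with τ = τ_on in a bout and τ_off in a rest. Amplitude and one Tp1 are then fitted by least squares. Assumed, because the protocol gives no values: τ_on, τ_off, amplitude 1.8, baseline 0.5 and the handling of the baseline.

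**Step 3: a difference in recovery only** (onset 45 s, recovery raised from 55 to 65 s).

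| Baseline | Tp1 before | Tp1 after | Share of the 10 s entering Tp1 |
|---|---|---|---|
| fitted | 49.5 | 54.2 | 4.7/10 = 47% |
| held at true value | 53.1 | 61.0 | 7.9/10 = 79% |
| no baseline term | 69.1 | 76.8 | 7.7/10 = 77% |

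Over onsets of 40 to 50 s and recoveries of 50 to 80 s, the share is 41% to 51% (fitted) or 71% to 82% (held). A free Td does not absorb it: the best Td is 0 at 45/55 and 45/65. In the pilot table Td is 0 in four participants and 0.061 in the fifth.

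**Step 4: cancellation.** Start from onset 50 s and recovery 55 s, and make onset 5 s faster. Tp1 stays at 52.5 s if recovery slows to 61.3 s (baseline fitted), or at 54.1 s if it slows to 56.2 s (held).

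**Step 5: would the planned model ranking reveal it?** FPE = MSE·(1 + d/N)/(1 − d/N), so one more parameter pays if it lowers the residual sum of squares by more than about 2 noise variances. Take noise SD 0.3, near the median pilot RMSE (0.302); the variance is 0.09.

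- At 45/55 with baseline fitted, the symmetric model's misfit is 0.22, and 0.22/0.09 = 2.4. One participant's FPE then picks the on/off model with probability about Φ(√2.4 − √2) = Φ(0.13) = 55%, little better than a coin toss.
- At 45/65 the misfit is 0.42% of MSE, or 0.0042 × 1,800 = 7.6, and the probability is about Φ(√7.6 − √2) = Φ(1.34) = 91%.
- With the baseline held, 45/55 gives 0.94/0.09 = 10.4, so separation is easier.
- Pooled over 90 participants at 45/55 (fitted), the expected reduction is 90 × (2.4 + 1) = 306 against a penalty of 2 × 90 = 180. Its SD is √[2 × (90 + 2 × 216)] = 32, with 216 = 90 × 2.4. The margin is (306 − 180)/32 = 3.9 SDs.

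**Step 6: price of two time constants.** At 45/65 with baseline fitted, the standard errors under white noise are 1.78 s for Tp1 and 4.64 s for the off constant, the widest of the cases tried. The interval ratio at SD 7.6 is √(7.6² + 4.64²)/√(7.6² + 1.78²) = 8.90/7.81 = 1.14. Across on/off pairs 45/55, 45/65 and 40/60, the widening is about 1% to 14%. It reaches about a third if the SD is 4.6 s, or at 3 s sampling with SD 7.6 s.

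**The case against.** The strongest reply is that the on/off outcomes do not depend on Tp1. They come from the raw breath data, are summarised in 6.I.2, and enter the 6.I.3 regressions on puberty and physical activity. This stands. A reader might infer that recovery has no analysis at all, or that asymmetric kinetics are ruled out; the text supports neither.

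Second, the 6.I.1 comparison is secondary, follows the choice of a functional form, and gives its efficiency reading only as an example. If an asymmetric form were chosen, its parameters would naturally replace Tp1. This also stands and lowers the weight of the point. But FPE and MSE rank only the models that are tried, and nothing in the text ensures that an on/off form is among them.

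Third, Section 1, item 2 does state the child–adult intent, so it would be wrong to say that the comparison is not planned. What is missing is its link to 6.I.1, where developmental stage is set against Kp, Tp1 and Td. No listed aim calls for on/off times by sex; that part rests on 6.I.1 having chosen sex as a comparison.

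Fourth, the lack of a baseline term could be read as an error in the equation. It is not shown to be one: a transfer function describes dynamics, and an offset is commonly handled in data preparation. The no-baseline Tp1 of 69 to 77 s also lies above every pilot value (48.4 to 67.0 s). Baseline handling matters here only because it changes which phase Tp1 mainly reflects.

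Last, the sizes rest on assumed asymmetry. If onset and recovery times were nearly equal in every group, little would be lost.

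**Conclusion.** The point holds in limited form. The primary outcome separates onset from recovery, but the written sex and developmental-stage comparison uses a model that cannot separate them, and the example reads its single time constant as overall efficiency. Puberty is better covered, through the 6.I.3 regression.

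Under the assumed values, about 47% to 79% of a recovery-only difference enters Tp1. A 10 s recovery difference would shift it by 4.7 to 7.9 s, against a pilot between-subject SD of 7.6 s (five participants). The direction of the problem follows from the model; its size does not come from the protocol.

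Naming candidate models is detail that a separate analysis plan, not at hand, may supply. What can be judged here is that the parameters and the interpretation fixed in 6.I.1 do not match the stated primary outcome. Confidence is medium, and the change is a cheap improvement.

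**What to change.** In Section 6.I.1:

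1. Make the sex, pubertal and developmental-stage comparisons on the on- and off-transient response times already defined as primary (or on separate Tp1_on and Tp1_off), whichever model form is selected.
2. Include a model with separate on and off time constants among the variations. Judge it against the symmetric one by fit and cross-validation pooled over participants, since FPE in a single participant would often not separate the two.
3. Limit the efficiency reading of any time constant to the phase it describes.

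The cost is a few sentences and a little more analysis. No extra sessions or recordings are needed, and the target of 90, which rests on experience rather than a formula, is unaffected. Intervals per time constant become somewhat wider: about 1% to 14% at the pilot SD, and up to about a third in the less favourable cases. These figures assume white noise; pilot fits of 37% to 56% suggest that residuals may also contain misfit, so they may be optimistic.
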